10 DATA AND SAFETY MONITORING

Phase I studies will be reviewed at the scheduled Roswell Park Early Phase Clinical Trials (EPCT) meetings and the minutes are forwarded to the IRB for review.

The Roswell Park Data Safety Monitoring Committee will assess the progress of the Phase IIb portion of the study, the safety data, and critical efficacy endpoints. The DSMC will review the study annually and will make recommendations that include but not limited to; (a) continuation of the study, (b) modifications to the design (c) or termination of the study.

11 STATISTICAL METHODOLOGY

11.1 Primary Objective

For the Phase I component of the study 2 cohorts will be examined as described in the body of the project description. The following decision rules will be followed: (i) If 0/3 dose limiting toxicities (DLTs) are observed proceed to enroll 3 more patients (ii) If 1/3 DLTs are observed enroll 3 more patients at the same treatment regimen. If 0/6 or 1/6 DLTs are observed, declare the regimen safe and as the maximum tolerated dose combination (MTD) of INCB024360 in combination with the vaccine. If at least 2/3 or 2/6 DLTs are observed in Cohort 1, stop and de-escalate INCB024360 to 100 mg BID in Cohort -1. If at least 2/3 or 2/6 DLTs are observed in Cohort -1, stop and de-escalate INCB024360 to 50 mg BID in Cohort -2. It is anticipated that the probability of a DLT is rare in this setting. A Monte Carlo study using 10,000 replications was conducted. If the $\text{Prob(DLT)} = 0.2$ for Cohort 1 and $\text{Prob(DLT)} = 0.1$ for Cohort -1 or Cohort -2 then the expected sample size for the Phase I component of this study is 5.1 patients and the probability of declaring Cohort 1 as the MTD is 0.71 and the probability of declaring Cohort -1 or Cohort -2 as the MTD is 0.22. If the $\text{Prob(DLT)} = 0.1$ for Cohort 1 and $\text{Prob(DLT)} = 0.05$ for Cohort -1 or Cohort -2 then the expected sample size for the Phase I component of this study is 4.0 patients and the probability of declaring Cohort 1 as the MTD is 0.91 and the probability of declaring Cohort -1 or Cohort -2 as the MTD is 0.08. If the $\text{Prob(DLT)} = 0.5$ for Cohort 1 and $\text{Prob(DLT)} = 0.1$ for Cohort -1 or Cohort -2 then the expected sample size for the Phase I component of this study is 6.1 patients and the probability of declaring Cohort 1 as the MTD is 0.17 and the probability of declaring Cohort -1 or Cohort -2 as the MTD is 0.47.

The Phase IIb component of this trial will consist of a randomized parallel design of $n = 25 + 25 = 50$ patients with treatment arms (i) DEC205mAb-NY-ESO-1 fusion protein (CDX-1401) with adjuvant poly-ICLC and (ii) INCB024360 in combination with the DEC205mAb-NY-ESO-1 fusion protein (CDX-1401) with adjuvant poly-ICLC. Stratification will be on clinical site (Roswell Park, U. of Pittsburgh). The primary endpoint will be progression free survival. Baseline is defined as the time following the treatment free interval, which can span 0 - 2 months, as described in Iasonos et al.[1] The primary analysis will be carried forth using a Cox proportional hazards model with factors corresponding to treatment and a continuous covariate adjustment for the length of the treatment free interval and a stratification factor for clinical site. Permuted blocked random assignment with block sizes of 4 and an allocation ratio of 1:1 for DEC205mAb-NY-ESO-1 fusion protein (CDX-1401) with adjuvant poly-ICLC alone versus INCB024360 in combination with the DEC205mAb-NY-ESO-1 fusion protein (CDX-1401) with adjuvant poly-ICLC stratified by clinical site..

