	
poly-ICLC (Day 1 and Day 2) for each 28 day cycle for a total of 5 cycles, and daily oral INCB024360 50 mg BID (Cohort -1) starting on Day 1 for 7 cycles.
 
Phase IIb:
 
The Phase IIb component of this trial will consist of a randomized parallel design of n=25+25=50 patients =50 patients with treatment arms: (i) DEC205mAb-NY-ESO-1 fusion protein (CDX-1401) with adjuvant poly-ICLC alone and (ii) INCB024360 in combination with the DEC205mAb-NY-ESO-1 fusion protein (CDX-1401) with adjuvant poly-ICLC. Stratification will be on clinical site (Roswell Park, U. of Pittsburgh).
 
The primary endpoint will be progression free survival. Baseline is defined as the time following the treatment free interval, which can span 0 - 2 months, as described in Iasonos et al.[1] The primary analysis will be carried forth using a Cox proportional hazards model with factors corresponding to treatment and a continuous covariate adjustment for the length of the treatment free interval and a stratification factor for clinical site.
 
Exploratory Cohort Roswell Park site ONLY:
 
An additional exploratory cohort (N=6) receiving 4 cycles of sirolimus in combination with DEC205mAb-NY-ESO-01 fusion protein (CDX-1401) with adjuvant poly-ICLC will be added to supplement the secondary objectives, which will aid in planning the next phase of the investigation. This will not affect the randomized component of the study as enrollment to the randomized Phase IIb at Roswell Park only will be suspended temporarily until the 6 patients are enrolled.

Accrual Target / Duration	
Phase I: 3 – 12 patients
 
Phase IIb: 50 patients
 
Exploratory Cohort: 6 patients
 
The duration of patient enrollment is expected to be 8 years. Patients in Phase I and Phase IIb are expected to participate in the study for approximately 28 weeks of active therapy. Patients in the exploratory cohort are expected to participate in the study for approximately 20 weeks of active therapy.

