6.2 Cohort Management

A patient will be considered to have completed treatment with study medications following completion of 7 cycles of treatment and the final assessments at treatment discontinuation. An eligible patient receiving at least 1 dose of the investigational agents, DEC205mAb-NY-ESO-1 fusion protein (CDX-1401) given with adjuvant poly-ICLC with or without INCBO24360, will be considered evaluable for safety. A patient that completes 2 or more cycles of treatment will be eligible for the analysis of immune response. Patients who do not complete the study through Day 29 for reasons other than dose limiting toxicities (DLTs) will be replaced. All patients will be included in the analysis of results.

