6.3 Dose Modification

No dose adjustments during this study are planned for the DEC205mAb-NY-ESO-1 fusion protein (CDX-1401) given with adjuvant poly-ICLC vaccine.

In the event of excessive discomfort, skin breakdown or desquamation, or a Grade 3 treatment-related systemic toxicity following CDX-1401 and poly-ICLC dosing, administration of adjuvant (poly-ICLC) on the subsequent day should be omitted. Provided the toxicity has resolved to Grade 2 or less, the next monthly treatment may be administered as scheduled at a new administration site.

Refer to **Section 11.1** for the Phase I parameters and decisions rules for INCBO24360 dose adjustments.

Dose adjustments for hematological toxicity will be based on the blood counts obtained at baseline and after each 28-day cycle of DEC205mAb-NY-ESO-1 fusion protein (CDX-1401) given with adjuvant poly-ICLC and with or without INCBO24360.

If at least 2/3 or 2/6 DLT's are observed in cohort one, the dose of INCBO24360 will be reduced from 300 mg to 100 mg BID. If at least 2/3 or 2/6 DLT's are observed in Cohort 1, the dose of INCBO24360 will be reduced from 100 mg to 50 mg BID in Cohort 2. The study will continue at this dose level.

Dose modification for INCBO24360 are based on decision rules in **Section 11.1**.

Patients will be withdrawn from the study if they fail to recover to Grade 2, CTCAE Version 4.0, from a treatment-related toxicity within 4 weeks (leading to treatment delay of \geq 4 weeks. For patients that recover in $<$ 4 weeks, when toxicities have resolved to Grade 2 or lower, INCBO24360 may be restarted. In patients that recover from toxicity in less than 4 weeks and who restart therapy, the next treatment cycle will be scheduled for 4 weeks later. Additional cycles will also follow at 4 weeks intervals.

Dose modification for Phase IIB (INCBO24360 cohorts)

When an INCBO24360 toxicity is observed, dose administration may be delayed/interrupted to allow for recovery from toxicity. INCBO24360 may be restarted at a reduced dose of 100 mg. po BID. Please contact the PI for attribution.

Based on the phase I safety review, INCBO24360 300 mg. po BID x 7 cycles has been selected for the phase IIB dose. Dose modification criteria will be defined as any Grade 3 or higher treatment-related (i.e. definitely, probably, or possibly related) toxicity that occurs outside the DLT evaluation period including:

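### The nine Phase I operating characteristics in Section 11.1 do not belong to the decision rule printed with them; expected sizes of 5.1 and 4.0 are impossible under it

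*Combined protocol and SAP*

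**What the plan says.** The Phase I rule is in Section 11.1, and the synopsis repeats it. After three patients without a DLT the instruction is "i) If 0/3 dose limiting toxicities (DLTs) are observed proceed to enroll 3 more patients"; one DLT in three also leads to three more patients. Acceptance comes only at six: "If 0/6 or 1/6 DLTs are observed, declare the regimen safe". Otherwise, "If at least 2/3 or 2/6 DLTs are observed in Cohort 1, stop and de-escalate INCB024360 to 100 mg BID in Cohort -1", and the same trigger in Cohort -1 leads to 50 mg BID in Cohort -2.

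The same paragraph then reports a Monte Carlo study of 10,000 replications in three scenarios. For DLT probabilities of 0.2 in Cohort 1 and 0.1 below it, "the expected sample size for the Phase I component of this study is 5.1 patients", with MTD probabilities of 0.71 (Cohort 1) and 0.22 (Cohort -1 or -2). For 0.1 and 0.05 the figures are 4.0, 0.91 and 0.08. For 0.5 and 0.1 they are 6.1, 0.17 and 0.47.

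The surrounding text is not consistent:
- Section 11.1 opens with "For the Phase I component of the study 2 cohorts will be examined", but its rule and Table 1 have three cohorts, each of 3 to 6 patients in Table 1.
- The synopsis gives accrual as "Phase I: 3 – 12 patients"; Section 3.1.1 gives 3 to 18.
- Section 11.1 does not say what follows two or more DLTs in Cohort -2. Section 6.3, after describing the step down to 50 mg, adds "The study will continue at this dose level".

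**The concern.** A mean cannot lie below the minimum. If no cohort can be accepted before six patients, and failure of Cohort 1 after three leads to at least three more in Cohort -1, then an average Phase I of 5.1 or 4.0 patients cannot come from this rule. The simulation must have been run on some other rule, which puts all nine figures in doubt.

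These are the only operating characteristics given for the rule that selected the Phase IIb dose. If they describe a different design, the protocol misstates how many patients Phase I was expected to need, how often 300 mg BID would be accepted when too toxic, and how often de-escalation would end in a usable dose.

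**Working it through.** **Inputs.** The rule, the three pairs of DLT probabilities and the 10,000 replications all come from Section 11.1. I assume independent DLTs, evaluation in blocks of three, all patients evaluable, and Cohort -2 enrolling and able to fail by the same rule.

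**Reproducing the plan's figures.** They can be reproduced, but from a rule that is not printed: accept at 0/3, or at 1/3 followed by 0/3; use two cohorts; de-escalate once, and only on exactly 2 DLTs. In the first scenario:
- P(Cohort 1) = 0.512 + 0.384 × 0.512 = 0.709
- P(exactly 2 DLTs) = 0.096 + 0.384 × 0.384 = 0.2435
- E[N] = (3 + 3 × 0.384) + 0.2435 × (3 + 3 × 0.243) = 5.06
- P(Cohort -1) = 0.2435 × 0.9061 = 0.221

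The other scenarios give 4.02 / 0.906 / 0.084 and 6.048 / 0.172 / 0.467. Eight of the nine agree with the protocol to the printed digit. The ninth (6.048 against 6.1) is within simulation error (standard error 0.023). That this rule was the one simulated is an inference; no code is shown.

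**The floor under the printed rule.** Accepting Cohort 1 takes 6 patients. Failing it takes at least 3, followed by at least 3 in Cohort -1. Every completed path therefore uses at least 6. Suppose instead that a cohort could stop at its second DLT. A failing path would still use at least 2 + 2 = 4, so E[N] is at least 6 × 0.6554 + 4 × 0.3446 = 5.31 in the first scenario and 6 × 0.8857 + 4 × 0.1143 = 5.77 in the second. Both exceed the stated 5.1 and 4.0.

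**Exact values for one cohort.**
- Acceptance: a(p) = (1−p)^6 + 6p(1−p)^5. At most 1 DLT in six implies at most 1 in the first three.
- Failure at three: s(p) = 3p²(1−p) + p³
- Expected cohort size: n(p) = 6 − 3s(p)

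| p | a(p) | s(p) | n(p) |
|---|---|---|---|
| 0.05 | 0.9672 | 0.00725 | 5.978 |
| 0.1 | 0.8857 | 0.028 | 5.916 |
| 0.2 | 0.6554 | 0.104 | 5.688 |
| 0.5 | 0.1094 | 0.5 | 4.500 |

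**Whole Phase I, three cohorts.** Write p1 for Cohort 1, p2 for the lower cohorts, and b = 1 − a.
- E[N] = n(p1) + b(p1)·n(p2) + b(p1)·b(p2)·n(p2)
- P(lower cohort is MTD) = b(p1)·[1 − b(p2)²]

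For 0.2/0.1: E[N] = 5.688 + 0.3446 × 5.916 + 0.3446 × 0.1143 × 5.916 = 7.96, and P(lower) = 0.3446 × (1 − 0.0131) = 0.340. With two cohorts, the last term of E[N] drops out and P(lower) = b(p1)·a(p2).

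| P(DLT) | Quantity | Stated | Exact, three cohorts | Exact, two cohorts |
|---|---|---|---|---|
| 0.2/0.1 | E[N] | 5.1 | 7.96 | 7.73 |
| | P(Cohort 1) | 0.71 | 0.655 | 0.655 |
| | P(lower) | 0.22 | 0.340 | 0.305 |
| 0.1/0.05 | E[N] | 4.0 | 6.62 | 6.60 |
| | P(Cohort 1) | 0.91 | 0.886 | 0.886 |
| | P(lower) | 0.08 | 0.114 | 0.111 |
| 0.5/0.1 | E[N] | 6.1 | 10.37 | 9.77 |
| | P(Cohort 1) | 0.17 | 0.109 | 0.109 |
| | P(lower) | 0.47 | 0.879 | 0.789 |

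A 200,000-run simulation of the three-cohort rule gave E[N] of 7.95, 6.62 and 10.37, and a minimum of 6 when Cohort 1 was accepted.

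**Is it simulation noise?** P(Cohort 1) does not depend on the number of cohorts, so it is the cleanest test. Its standard error at 10,000 runs is √(a·b/10,000) = 0.0048, 0.0032 and 0.0031. Taking the lowest value that rounds to each stated figure:
- (0.705 − 0.6554)/0.0048 ≈ 10
- (0.905 − 0.8857)/0.0032 ≈ 6
- (0.165 − 0.1094)/0.0031 ≈ 18

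Noise is excluded.

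**A further sign.** In the third scenario the stated probabilities leave 1 − 0.17 − 0.47 = 0.36 for no MTD, although the lower doses have a DLT rate of only 0.1. The printed rule leaves 0.8906 × 0.1143² = 0.012 with three cohorts.

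**Sensitivity to the Cohort -2 outcome.** With failure possible there, the chance of no MTD is 0.0045, 0.0001 and 0.012. If 50 mg is kept whatever happens, that chance is 0 and P(lower) = b(p1) = 0.345, 0.114 and 0.891. If Cohort -2 needs no evaluation patients, E[N] is 7.7, 6.6 and 9.8. None of these approaches the stated figures.

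**The case against.** The strongest reply concerns weight. Phase I is complete, 300 mg BID has been selected (Table 1 and Section 6.3), and neither the Phase IIb size nor any analysis uses these numbers. The printed rule is also the more cautious one: it expands after 0/3, and it accepts a dose with a 50% DLT rate with probability 0.11 rather than 0.17. Patients were therefore better protected than the text implies. All of this stands, and it limits the consequence. It does not make the figures correct.

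A second reply is that a minimum of 3 patients is not absurd as an enrolment range, because the stopping rules in Section 6.3.2 or the committee review in Section 11.5 could end Phase I early. This also stands: six is the floor for a Phase I run to completion. The quoted means are presented as properties of the DLT rule, however, and under that rule six applies.

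A third is that Section 6.3 does not expressly address DLTs seen at 50 mg. Its cohort labels are garbled, and its closing sentence follows the step down from 100 mg. Read literally, that sentence keeps the study at 50 mg, but it is not a clear rule for Cohort -2 failure. That is a reason to write one.

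Finally, if 50 mg needed no evaluation patients the maximum would be 12, as in the synopsis. Table 1 lists 3 to 6 patients for Cohort -2, which supports 18.

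**Conclusion.** The concern holds. Two of the three expected sizes are impossible under the printed rule, and all nine figures differ from its exact values whether two or three cohorts are counted. Across both readings the expected size is understated by 2.6 to 4.3 patients. P(Cohort 1 is MTD) is overstated by 0.02 to 0.06. The probability of ending at a lower dose is understated, most of all when 300 mg BID is truly too toxic: 0.47 against 0.88 with three cohorts, or 0.79 with two.

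The impossibility of 5.1 and 4.0 needs only the printed rule and a Phase I run to completion. The exact replacement values rest on the assumptions listed with the inputs. The correction should be made, but it casts no doubt on the dose chosen or on Phase IIb.

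**What to change.** - Replace the nine figures in Section 11.1 with those for the printed rule. For three cohorts, as E[N] / P(Cohort 1) / P(lower): 8.0 / 0.66 / 0.34; 6.6 / 0.89 / 0.11; 10.4 / 0.11 / 0.88.
- State what follows two or more DLTs in Cohort -2: either the regimen fails, or 50 mg is kept. If it is kept, use 0.345, 0.114 and 0.891 for the lower-cohort probabilities. Correct the cohort labels in Section 6.3 to match.
- Say three cohorts, not two, at the start of Section 11.1.
- Give Phase I accrual as 6 to 18 evaluable patients in both the synopsis and Section 3.1.1. Add that replacements come on top, since "Patients who do not complete the study through Day 29 for reasons other than dose limiting toxicities (DLTs) will be replaced".
- Use the corrected figures wherever the Phase I design is reported.

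The cost is a text correction. The selected dose, the Phase IIb sample size and the remaining accrual do not change.

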3 METHODOLOGY

3.1 Study Design

This is an open-label, Phase I/IIb study of the IDO inhibitor, INCB024360, in combination with DEC205mAb-NY-ESO-1 fusion protein (CDX-1401) given with adjuvant poly-ICLC in patients with NY-ESO-1 or LAGE-1 expressing epithelial ovarian, fallopian tube, or primary peritoneal cancer who are in remission.

For the Phase I component of the study, eligible patients will receive a fixed intracutaneous dose of DEC205mAb-NY-ESO-1 fusion protein (CDX-1401) (Day 1) given with subcutaneous adjuvant poly-ICLC (Day 1 and Day 2) for each 28 day cycle for a total of 5 cycles; and Cohort 1 patient enrollment will begin INCB024360 at a fixed daily dose of 300 mg BID orally (Cohort 1) for a total of 7 cycles. Based on the decision rules for DLTs, patients may be enrolled into Cohort -1. Cohort -1 will receive DEC205mAb-NY-ESO-1 fusion protein (CDX-1401) (Day 1) given with adjuvant poly-ICLC (Day 1 and Day 2) for each 28 day cycle for a total of 5 cycles, and daily oral INCB024360 100 mg BID (Cohort -1) starting on Day 1 for 7 cycles. Based on the decision rules for DLTs, patients may be enrolled into Cohort -2. Cohort -2 will receive DEC205mAb-NY-ESO-1 fusion protein (CDX-1401) (Day 1) given with adjuvant poly-ICLC (Day 1 and Day 2) for each 28 day cycle for a total of 5 cycles, and daily oral INCB024360 50 mg BID (Cohort -1) starting on Day 1 for 7 cycles.

After completing 1 cycle of treatment in the last patient from Cohort 1 (or Cohort -1 or Cohort -2), accrual into the randomized Phase IIb study (Cohort 2) will begin at the dose of INCB024360 that is determined to be safe in the Phase I trial (300 mg BID versus 100 mg BID versus 50 mg BID) in combination with CDX-1401. This is a randomized parallel design employing randomization for each patient enrolled to 1 of 2 groups (**Table 1**). Treatment cohorts include (i) DEC205mAb-NY-ESO-1 fusion protein (CDX-1401) given with adjuvant poly-ICLC alone and (ii) INCB024360 plus DEC205mAb-NY-ESO-1 fusion protein (CDX-1401) given with adjuvant poly-ICLC.

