3.1.1 Target Accrual and Study Duration

The Phase I component of this study will enroll 3 -18 patients and 50 patients for the Phase IIb component. Six patients will be enrolled in the additional exploratory cohort. Patients will be enrolled at Roswell Park and participating sites. The exploratory cohort applies to the Roswell Park site only. Accrual is expected to take approximately 8 years. Patients in Phase I and Phase IIb are expected to participate in this study for approximately 28 weeks of active therapy. Patients in the exploratory cohort are expected to participate in this study for approximately 20 weeks of active therapy.

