11.1.1 Sample Size Justification

We assume a median PFS of 8 months for the INCB024360 alone arm. For the purpose of our simulation study we utilized the simplifying assumption that the covariate adjustment for time between treatment and clinical site are not significant. We also assume a constant hazard rate and a 9 month accrual period with up to 5 years of follow-up. The detectable effect size for the INCB024360 in combination with the DEC205mAB-NY-ESO-1 fusion protein (CDX-1401) arm

different from the INCB024360 alone arm is a PFS of 16 months (or a 2 to 1 risk ratio) with a power estimated from simulation of 0.70. From a practical consideration n = 25 patients per arm is anticipated to be the maximum for which we can accrue during the timeframe of this study.

An additional exploratory cohort (N=6) receiving the same DEC205mAb-NY-ESO-01 fusion protein (CDX-1401) with adjuvant poly-ICLC but in combination with sirolimus in place of INCB024360 will be added to supplement the secondary objectives, which will aid in planning the next phase of the investigation.

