2. SUBJECT REGISTRATION

The subject completes the **Gender, Race, and Ethnicity Form** and this is placed in the study binder.

Roswell Park does not grant exceptions to eligibility criteria.

Phase 2 Protocol Registration Instructions

The **Subject Enrollment Log** must be faxed or emailed to the Roswell Park Network Office within 24 hours of the date the subject is consented. Once the Investigator has determined that eligibility has been met, complete the **Subject Registration Form and fax or email** it to the Roswell Park Network Monitor at [contact].

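### A single, printed block size of 4 within site lets a team that tallies its open-label assignments deduce about a third of them in advance

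*Combined protocol and SAP*

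**What the plan says.** Section 11.1 gives the randomisation method for Phase IIb as "Permuted blocked random assignment with block sizes of 4 and an allocation ratio of 1:1". The synopsis and Section 11.1 both add "Stratification will be on clinical site (Roswell Park, U. of Pittsburgh"), so each sequence of blocks runs within one site. Section 3.1 opens with "This is an open-label, Phase I/IIb study of the IDO inhibitor, INCB024360". In Table 1 one randomised arm takes twice-daily oral INCB024360 for seven cycles and the other takes none, so every assignment is visible to the treating team once it is made.

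On sample size, Section 11.1.1 says "From a practical consideration n = 25 patients per arm is anticipated to be the maximum", which makes 50 in all. The split between sites is not given; Section 3.1.1 says only "Patients will be enrolled at Roswell Park and participating sites".

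On registration, Appendix J (instructions for network sites), item 2, reads "Once the Investigator has determined that eligibility has been met, complete the" registration form, which then goes to the coordinating centre. The documents do not say who holds the list, how the next assignment is concealed, or whether the block size is kept from enrolling staff. A separate randomisation procedure may exist, so the supported statement is that no such protection is described.

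**The concern.** With one known block size and visible past assignments, the end of each block can be worked out by counting. Access to the list is not needed, and central assignment would not prevent it.

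Foreknowledge matters when staff have discretion over who is enrolled and when. Section 4.2 has an exclusion that turns on the investigator's opinion (criterion 16). Section 4.1 admits patients treated for primary or recurrent disease, with no evidence of disease or with minimal residual disease. These features plausibly carry different prognoses, although the documents give no sizes. The primary Cox model in Section 11.1 contains treatment, the length of the treatment-free interval and site. If knowledge of the next assignment led to an imbalance in recurrence status or residual disease, the planned analysis would not correct it. With 25 patients per arm, a few such patients could shift the comparison.

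**Working it through.** The plan states no predictability figure, so there is none to reproduce.

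**Inputs.** Block of 4 at 1:1, so two A and two B (Section 11.1); blocks within site (Section 11.1); 50 patients (Section 11.1.1). The site split is not stated, so every split over the two named sites was computed. Assumption: staff know the block size and keep a complete tally of their site's assignments.

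**Step 1, certain knowledge in a complete block.** An assignment is certain once the earlier ones in its block have used up one arm. The six orders are equally likely:

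| Order | Positions certain | Count |
|---|---|---|
| AABB, BBAA | 3rd and 4th | 2 each |
| ABAB, ABBA, BAAB, BABA | 4th | 1 each |

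Total = 2×2 + 4×1 = 8 of 24 positions, or 33.3% (1.333 per block). The fourth position is always known and the third is known with probability 2/6 = 1/3. In general, a 1:1 block of size 2m gives a share of 1/(m+1), which is 1/3 for m = 2.

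**Step 2, best guess.** Guess the arm that is behind in the block. The chances of being right at positions 1 to 4 are 1/2, 2/3, (1/3)×1 + (2/3)×(1/2) = 2/3, and 1. The sum is 17/6, and (17/6)/4 = 17/24 = 70.8%, against 50% by chance.

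**Step 3, the planned 50 with incomplete last blocks.**
- 25/25 split: each site has 6 complete blocks plus one patient. Certain: 2 × 6 × 4/3 = 16.0, or 32.0%. Best guess: 12 × 17/6 + 2 × 1/2 = 35 of 50, or 70.0%.
- Lowest case, for example 23/27: 5 and 6 complete blocks, with three patients left over at each site. Certain: 11 × 4/3 + 2 × 1/3 = 15.33, or 30.7%.
- Over all splits, certain knowledge runs from 30.7% to 32.0% and the best guess stays close to 70%.

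**Step 4, alternatives.** Fixed blocks of 6 or 8 would still give 1/4 = 25% or 1/5 = 20%. Mixed sizes were simulated with 25 patients per site, assuming staff know the set of sizes but not their order and update their belief after each assignment:

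| Scheme | Known with certainty | Best guess right |
|---|---|---|
| Fixed 4 (current) | about 32% | about 70% |
| Random 4/6 | about 6% | about 68% |
| Random 4/6/8 | about 2% | about 67% |

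Of 50 patients, that is about 16 certain assignments now, 0.06 × 50 = 3 with 4/6, and 0.02 × 50 = 1 with 4/6/8.

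**The case against.** **The change leaves most guessing intact.** The best-guess rate drops only from about 70% to about 67%, so someone willing to act on a guess loses little. This stands, and it limits the claimed benefit to removing certainty.

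**Opportunity is limited.** Steering needs patients who can be chosen between or delayed. Section 3.1.1 expects about 8 years of accrual. If all of that applied to Phase IIb and sites enrolled equally (an assumption), the rate would be 50/8 = 6.25 patients a year, about 3.1 per site, and a block would take 4/3.1 = 1.3 years. But the 8 years also cover Phase I and the exploratory cohort, and the power calculation in Section 11.1.1 assumes 9 months. At that pace each site would enrol 25/9 = 2.8 a month and fill a block in about 1.4 months. The 28-day baseline window (Table 3, footnote 1) and the 0 to 2 month treatment-free interval (Section 11.1) limit delay without ruling it out. The objection stands in part.

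**There is a partial safeguard.** Appendix J requires the enrolment log to be sent within 24 hours of consent and allows no eligibility exceptions. Steering after consent would therefore leave a trace. The log does not record who was never approached, and it does not remove the foreknowledge.

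**Stronger readings that the documents do not support.** A reader might infer that having only two sites raises predictability. It does not; what matters is that blocks run within a site whose team sees the whole sequence. A reader might also fold in unblinded calling of progression. That is a separate bias, which block size neither causes nor cures.

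**Conclusion.** The point holds as a modest, inexpensive design improvement. One printed block size of 4, run within site in an open-label trial, makes 33% of assignments in complete blocks (31 to 32% of the planned 50) deducible with certainty and allows about 70% correct guessing. The 33% is exact. It assumes that staff know the size and keep a full tally, and the documents do not show that anyone does.

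A reader might go further and infer that the trial's false-positive rate is inflated by some stated amount. The documents do not support a figure. It would depend on the prognostic mix, the strength of the prognostic factor, the site split, how often and in which direction staff acted, and the alpha and sidedness of the test. None of these is given. Nor does anything show that steering has taken place. The supported conclusion is avoidable exposure to selection bias, in a small comparison whose model would not correct for disease setting or residual disease.

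**What to change.** For any assignments still to be made, generate a new list with randomly varying block sizes within site, for example 4, 6 and 8. Replace the block-size wording in Section 11.1 with a statement that permuted blocks of varying size are used, and record the sizes only in a restricted randomisation file held by the statistician. The 1:1 ratio, stratification by site, analysis and sample size stay the same. Letting each site finish its open block before switching preserves balance, at the price of at most three more assignments per site under the old rule. Nothing undoes the disclosure for blocks already filled, and the documents do not establish whether randomisation is still open.

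The cost is one sentence and a new list. Final arms may depart from 25/25, which blocks of 4 do not guarantee either: 50 is not a multiple of 4, and incomplete last blocks at two sites can give 26/24. With sizes up to 8, the last block at each site could be at most 4 out, so the unlikely extreme is 29/21. Even then the relative information for the treatment comparison is about 4 × 29 × 21 / 50² = 0.974, a loss of under 3%.
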